8.4 Informed consent

The Principal Investigator(s) at each centre will:

- Ensure each patient is given full and adequate oral and written information about the nature, purpose, possible risk and benefit of the study
- Ensure each patient is notified that they are free to discontinue from the study at any time
- Ensure that each patient is given the opportunity to ask questions and allowed time to consider the information provided
- Ensure each patient provides signed and dated informed consent before conducting any procedure specifically for the study
- Ensure the original, signed Informed Consent Form(s) is/are stored in the Investigator's Study File
- Ensure a copy of the signed Informed Consent Form is given to the patient
- Ensure that any incentives for patients who participate in the study as well as any provisions for patients harmed as a consequence of study participation are described in the informed consent form that is approved by an Ethics Committee.

8.5 Changes to the protocol and informed consent form

Study procedures will not be changed without the mutual agreement of the International co-ordinating Investigator, National Co-ordinating Investigator, and the Principal Investigator and AstraZeneca.

If there are any substantial changes to the study protocol, then these changes will be documented in a study protocol amendment and where required in a new version of the study protocol (Revised Clinical Study Protocol).

The amendment is to be approved by the relevant Ethics Committee and if applicable, also the national regulatory authority approval, before implementation. Local requirements are to be followed for revised protocols.

AstraZeneca will distribute any subsequent amendments and new versions of the protocol to each Principal Investigator(s). For distribution to Ethics Committee see Section 8.3.

If a protocol amendment requires a change to a centre's Informed Consent Form, AstraZeneca and the centre's Ethics Committee are to approve the revised Informed Consent Form before the revised form is used.

If local regulations require, any administrative change will be communicated to or approved by each Ethics Committee.

8.6 Audits and inspections

Authorised representatives of AstraZeneca, a regulatory authority, or an Ethics Committee may perform audits or inspections at the centre, including source data verification. The purpose of an audit or inspection is to systematically and independently examine all study-related activities and documents, to determine whether these activities were conducted, and data were recorded, analysed, and accurately reported according to the protocol, Good Clinical Practice (GCP), guidelines of the International Conference on Harmonisation (ICH), and any applicable regulatory requirements. The investigator will contact AstraZeneca immediately if contacted by a regulatory agency about an inspection at the centre.

9. STUDY MANAGEMENT BY ASTRAZENECA

9.1 Pre-study activities

Before the first patient is entered into the study, it is necessary for a representative of AstraZeneca to visit the investigational study site to:

- Determine the adequacy of the facilities
- Determine availability of appropriate patients for the study
- Discuss with the investigator(s) (and other personnel involved with the study) their responsibilities with regard to protocol adherence, and the responsibilities of AstraZeneca or its representatives. This will be documented in a Clinical Study Agreement between AstraZeneca and the investigator.

9.2 Training of study site personnel

Before the first patient is entered into the study, an AstraZeneca representative will review and discuss the requirements of the Clinical Study Protocol and related documents with the

investigational staff and also train them in any study specific procedures and the WBDC system utilised.

The Principal Investigator will ensure that appropriate training relevant to the study is given to all of these staff, and that any new information relevant to the performance of this study is forwarded to the staff involved.

The Principal Investigator will maintain a record of all individuals involved in the study (medical, nursing and other staff).

9.3 Monitoring of the study

During the study, an AstraZeneca representative will have regular contacts with the study site, including visits to:

- Provide information and support to the investigator(s)
- Confirm that facilities remain acceptable
- Confirm that the investigational team is adhering to the protocol, that data are being accurately and timely recorded in the CRFs, that biological samples are handled in accordance with the Laboratory Manual and that study drug accountability checks are being performed
- Perform source data verification (a comparison of the data in the CRFs with the patient's medical records at the hospital or practice, and other records relevant to the study) including verification of informed consent of participating patients. This will require direct access to all original records for each patient (eg, clinic charts)
- Ensure withdrawal of informed consent to the use of the patient's biological samples is reported and biological samples are identified and disposed of/destroyed accordingly, and the action is documented, and reported to the patient.

The AstraZeneca representative will be available between visits if the investigator(s) or other staff at the centre needs information and advice about the study conduct.

9.3.1 Source data

Refer to the Clinical Study Agreement for location of source data.

9.4 Study agreements

The Principal Investigator at each/the centre should comply with all the terms, conditions, and obligations of the Clinical Study Agreement, or equivalent, for this study. In the event of any inconsistency between this Clinical Study Protocol and the Clinical Study Agreement, the terms of Clinical Study Protocol shall prevail with respect to the conduct of the study and the treatment of patients and in all other respects, not relating to study conduct or treatment of patients, the terms of the Clinical Study Agreement shall prevail.

Agreements between AstraZeneca and the Principal Investigator should be in place before any study-related procedures can take place, or patients are enrolled.

9.4.1 Archiving of study documents

The Investigator follows the principles outlined in the Clinical Study Agreement (CSA).

9.5 Study timetable and end of study

The end of the study is defined as ‘the last visit of the last patient undergoing the study’.

The study is expected to start in [REDACTED] and to end by [REDACTED]

The study may be terminated at individual centres if the study procedures are not being performed according to GCP, or if recruitment is slow. AstraZeneca may also terminate the entire study prematurely if concerns for safety arise within this study or in any other study with olaparib.

10. DATA MANAGEMENT BY ASTRAZENECA

Data management will be performed by AstraZeneca Data Management Centre staff.

The data collected through third party sources will be obtained and reconciled against study data.

Adverse events and medical/surgical history will be classified according to the terminology of the latest version the Medical Dictionary for Regulatory Activities (MedDRA). Medications will be classified according to the AstraZeneca Drug Dictionary. All coding will be performed by the Medical Coding Team at the AstraZeneca Data Management Centre.

Data queries will be raised for inconsistent, impossible or missing data. All entries to the study database will be available in an audit trail.

The data will be validated as defined in the Data Management Plan. Quality control procedures will be applied to each stage of data handling to ensure that all data are reliable and have been processed correctly.

When all data have been coded, validated, and locked, clean file will be declared. Any treatment revealing data may thereafter be added and the final database will be locked.

Data associated with biological samples will be transferred from laboratories internal or external to AstraZeneca. Data from external providers (e.g. central laboratories) will be validated as appropriate to ensure it is consistent with the clinical data and included in the final database. In the case of biomarker (tumour tissue or blood for exploratory analyses) data, the results of any analyses will not be recorded in the database, but information relating to the processing of the sample, including the original date of biopsy (historical tumour tissue

sample and the actual date the sample(s) were collected) will be recorded in the eCRF and database.

Exploratory genotype data generated in this study will be stored in the AstraZeneca genotyping LIMS database, or other appropriate secure system within AstraZeneca and/or third party contracted to work with AstraZeneca to analyse samples. The results from this exploratory genetic research may be reported in the CSR.

Some or all of the clinical datasets from the main study may be merged with the genetic data in a suitable secure environment separate from the clinical database.

Site staff will enter PRO booklet data into Medidata Rave.

11. EVALUATION AND CALCULATION OF VARIABLES BY ASTRAZENECA

11.1 Calculation or derivation of efficacy variable(s)

At each visit patients will be programmatically assigned a RECIST visit response of CR, PR, SD, PD, NE depending on the status of their disease compared to baseline and previous assessments, based on the BICR review. This will be repeated using the Investigator assessed RECIST data.

11.1.1 Primary endpoint

PFS is defined as the time from randomisation until the date of objective radiological disease progression according to RECIST 1.1 or death (by any cause in the absence of disease progression) regardless of whether the patient withdraws from randomised therapy or receives another anticancer therapy prior to disease progression. Patients who have not progressed or died at the time of analysis will be censored at the time of the latest date of assessment from their last evaluable RECIST assessment. However, if the patient progresses or dies after two or more missed visits, the patient will be censored at the time of the latest evaluable RECIST assessment. If the patient has no evaluable visits or does not have a baseline assessment they will be censored at day 1 unless they die within two visits of baseline (13 weeks allowing for visit window).

The PFS time will always be derived based on scan/assessment dates not visit dates.

RECIST assessments/scans contributing towards a particular visit may be performed on different dates. The following rules will be applied:

- (c) The date of progression will be determined based on the earliest of the scan dates of the component that triggered the progression for the adjudicated reviewer selecting PD or for either reviewer where both select PD as time point response and there is no adjudication for BICR data.

- (d) For investigational site assessments, date of progression will be determined based on the earliest of the RECIST assessment/scan dates of the component that triggered the progression.
- (e) When censoring a patient for PFS the patient will be censored at the **latest** of the RECIST assessment/scan dates contributing to a particular overall visit assessment.

Overall visit assessments will be determined for each assessment (scheduled or unscheduled) and will contribute to the derivation of PFS.

Objective progression is defined as at least a 20% increase in the sum of the diameters of the target lesions (compared to previous minimum sum) and an absolute increase of ≥ 5 mm, or an overall non-target lesion assessment of progression or a new lesion.

The primary analysis will be based on the blinded independent central review (BICR) of the radiological scans. A charter for the BICR will be developed in advance of the start of the study. A sensitivity analysis based on the programmatically derived PFS based on Investigator-recorded assessments will be carried out.

As a supportive summary to PFS, time to start of first subsequent cancer therapy or death will be assessed (see Section 12.2.3.1). Time to first subsequent cancer therapy or death is defined as the time from the date of randomisation to the earlier of first subsequent cancer therapy start date, or death date. Any patient not known to have had a further subsequent cancer therapy or death will be censored at the last known time to have not received subsequent cancer therapy.

11.1.2 Secondary endpoints

11.1.2.1 Overall Survival

Overall survival is defined as the time from the date of randomisation until death due to any cause. Any patient not known to have died at the time of analysis will be censored based on the last recorded date on which the patient was known to be alive.

Note: Survival calls will be made in the week following the date of Data Cut Off (DCO) date for the analysis, and if patients are confirmed to be alive or if the death date is post the DCO date these patients will be censored at the date of DCO.

11.1.2.2 Time from randomisation to second progression (PFS2)

Time from randomisation to second progression is defined as the time from the date of randomisation to the earliest of the progression event subsequent to that used for the primary variable PFS or death. The date of second progression will be recorded by the Investigator and defined according to local standard clinical practice and may involve any of; objective radiological or symptomatic progression or death. Second progression status will be reviewed every 8 weeks following the progression event used for the primary variable PFS (the first progression) and status recorded. Patients alive and for whom a second disease progression has not been observed should be censored at the last time known to be alive and without a

second disease progression, i.e. censored at the last progression assessment date if the patient has not had a second progression or death).

As a supportive summary to PFS2, time to start of second subsequent cancer therapy or death (TSST) will be assessed. Time to second subsequent cancer therapy or death is defined as the time from the date of randomisation to the earlier of the date of second subsequent cancer therapy start date, or death date. Any patient not known to have had a further second subsequent cancer therapy or death will be censored at the last known time to have not received second subsequent therapy.

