- Eribulin mesylate 1.4 mg/m² or Eribulin (active substance) 1.23mg/m² IV Day 1 and Day 8, repeat every 21 days

Duration of treatment

Patients will be randomised (using an IVRS/IWRS) in a 2:1 ratio to the treatments as specified below:

- Olaparib tablets po. 300 mg twice daily
- Physician's choice of chemotherapy (capecitabine, vinorelbine or eribulin)

Patients should continue to receive study treatment until objective radiological disease progression as per RECIST 1.1 as assessed by the investigator or unacceptable toxicity and they do not meet any other discontinuation criteria. Patients who are determined to have progressed according to RECIST 1.1 criteria by the Investigator will have scans centrally reviewed for confirmation of objective disease progression. If disease progression is not confirmed at central review an additional RECIST assessment will be requested at the next scheduled RECIST visit. Once patients have been discontinued from study treatment, other treatment options will be at the discretion of the investigator. Within this study, patients on chemotherapy will not be provided olaparib post discontinuation of study treatment.

All patients should continue RECIST assessments until documented evidence of objective radiological progression in accordance with RECIST 1.1, irrespective of treatment decisions

(i.e RECIST follow up until progression even if a patient discontinues study treatment prior to progression and/or receives a subsequent therapy prior to progression).

Outcome variable(s):

- Primary outcome variable
 - Progression Free Survival by BICR using RECIST 1.1.
- Safety outcome variables
 - Adverse Events (AE), physical examination, vital signs including blood pressure (BP), pulse, electrocardiogram (ECG) and laboratory findings including clinical chemistry and haematology
- Secondary outcome variables
 - Overall Survival
 - Time from randomisation to second progression, defined as objective radiological or symptomatic progression or death (PFS2)
 - Objective Response Rate by BICR using RECIST 1.1
 - PFS, PFS2 and OS based on patients with *gBRCA* mutations confirmed by the central test (only required if population differs from the ITT population)
 - Adjusted mean change from baseline in global QoL score from the EORTC-QLQ-C30 questionnaire
 - Pharmacokinetic sampling
- Exploratory outcome variables
 - Potential retrospective biomarker research

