Patients with unknown *BRCA* status must consent to provide 2 blood samples for germline *BRCA* testing and follow all local ethical procedures for such genetic testing. One sample will be used to test for *BRCA* mutations using the current commercial Myriad *BRCA* analysis test prior to study entry. The second blood sample from all tested patients (including those who do not have a *BRCA* mutation) is required for a bridging study to validate the companion diagnostic test for olaparib and/or assessment of current and future *BRCA* mutation assay(s). When the result from the Myriad test indicates the patient does have a deleterious or suspected deleterious germline *BRCA* mutation and the patient meets all other eligibility criteria, the patient can be randomised into the study.

After confirmation of eligibility patients will be randomised 2:1 to receive either:

- Arm A; olaparib 300 mg po twice daily
- Arm B; Physicians choice of chemotherapy (capecitabine, vinorelbine or eribulin)

Following randomisation patients in both treatment arms will attend clinic visits weekly for the first 3 weeks of treatment (Days 1, 8 and 15). Patients will then attend clinic visits every 3 weeks while receiving study treatment. Patients should continue to receive study treatment until objective radiological disease progression as per RECIST as assessed by the investigator,

unacceptable toxicity or as long as they do not meet any other discontinuation criteria as outlined in Section 5.8.

Patients will have RECIST assessments until evidence of objective disease progression irrespective of treatment decisions (i.e even if they discontinue study treatment and/or receive a subsequent therapy prior to progression). RECIST assessments will be scheduled every 6 weeks (+/- 1 week) from randomisation for the first 24 weeks and then every 12 weeks (+/- 1 week) thereafter.

All CT/MRI scans will be sent to an AstraZeneca appointed Clinical Research Organisation (CRO) for blinded independent central review. All treatment decisions will be based on site assessment of scans. Patients who are determined to have progressed according to RECIST 1.1 criteria by the Investigator will have scans centrally reviewed for confirmation of objective disease progression. If disease progression is not confirmed at central review an additional RECIST assessment will be requested at the next scheduled RECIST visit.

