6.2.6 Patient management post primary PFS analysis

The data cut off date for the statistical analysis for the primary objective of the study will be established when approximately 230 confirmed progression events (~75% maturity for PFS analysis) are expected to have occurred.

Patients on study treatment at the time of the data cut-off will continue to receive study treatment until they meet any discontinuation criteria as per Section 5.8.

Patients on study treatment will be followed for core safety assessments (haematology, clinical chemistry, AEs/SAEs, concomitant medications and study treatment dosing details).

Once the primary PFS analysis has been performed the collection of RECIST data for independent central review will cease. Patients who have not had an objective disease progression at the time of the data cut off for the primary PFS analysis should continue to have RECIST assessments until first objective disease progression is determined by the investigator. RECIST assessments should be performed every 12 weeks from the last assessment prior to the data cut off date. Following first progression patients should be assessed for second progression based on radiological or symptomatic progression or death. Patients will also be followed for information on vital status to obtain the data needed for the OS analysis.

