12.2.1 Multiplicity strategy for primary and key secondary endpoints

In order to describe the nature of the effects of olaparib compared to chemotherapy, PFS, PFS2, and OS will be tested at a two-sided significance level of 5%.

In addition to these planned analyses, which will be performed and reported in the CSR, in order to strongly control the type I error at 2.5% (one-sided) for key label claims, a multiple testing procedure (MTP) will be employed across the primary endpoint (PFS) and key secondary endpoints (PFS2 and OS).

A hierarchical testing strategy will be employed where PFS will be tested first using the full test mass (full test mass = alpha 2.5% one-sided) and key secondary endpoints of PFS2 and OS will then be tested using the MTP with a recycling strategy (i.e., the MTP will recycle the test mass to the endpoint not yet rejected in the hierarchy outlined in Figure 2). The MTP is detailed below.

Figure 2 Multiple Testing Procedure

PFS2 will only be tested if statistical significance is shown for PFS. OS will only be tested if statistical significance is shown for PFS2. This testing will occur at the time of the primary PFS analysis (approximately 230 PFS events), and again when there are approximately 60% deaths (approximately 190 OS events). The Lan and DeMets approach that approximates the O'Brien & Fleming spending function will be employed to preserve the overall 1-sided type-I error rate of 2.5% (Lan and DeMets 1983).

If the first analysis for PFS2 occurs at exactly 180 PFS2 events (58% overall data maturity predicted at the time of the primary PFS analysis), statistical significance for PFS2 will be declared if the null hypothesis for PFS is rejected and the observed one-sided p-value for

PFS2 is $p < 0.007$, which equates to a HR of ≤ 0.68 . The significance level at the final analysis will be determined based on the exact number of events at the time of the first and final analyses. If the first analysis for PFS2 occurs at exactly 180 PFS2 events and the final analysis occurs at exactly 255 PFS2 events, then the significance level to be applied at the final analysis will be 2.3%. Statistical significance for PFS2 will be declared if the observed p-value for PFS2 is $p < 0.023$, which equates to a HR of ≤ 0.77 .

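### PFS2 is defined from the BICR progression used for primary PFS, but the follow-up sections run it from the site-called first progression, so the definition can select the wrong event when readers disagree

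*Protocol*

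**What the plan says.** **Definition.** Protocol Section 11.1.2.2 measures PFS2 from randomisation to "the earliest of the progression event subsequent to that used for the primary variable PFS or death". Second progression is recorded by the investigator under local practice. Its status is reviewed 8-weekly from the event used for primary PFS, which the section labels the first progression.

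**The primary variable.** The synopsis lists it as "Progression Free Survival by BICR using RECIST 1.1", and Section 11.1.1 says "The primary analysis will be based on the blinded independent central review (BICR) of the radiological scans".

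**Follow-up.** Section 3.1 states "All treatment decisions will be based on site assessment of scans". Section 6.2.5 starts 8-weekly assessment for second progression after first objective progression. It also provides for that progression not being confirmed centrally, in which case a further scan at the next RECIST visit goes to central review. The first progression in that section is therefore the site's call. Section 6.2.6 says "Once the primary PFS analysis has been performed the collection of RECIST data for independent central review will cease", and that patients without progression at that point "should continue to have RECIST assessments until first objective disease progression is determined by the investigator", after which they are assessed for second progression.

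**Role in testing.** Under Section 12.2.1, PFS2 is tested only if PFS is significant, and OS only if PFS2 is significant. The section gives boundaries for 180 PFS2 events at the first analysis and for the case where "the final analysis occurs at exactly 255 PFS2 events".

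**The concern.** The definition and the follow-up sections use different events as first progression, and nothing reconciles them. Section 12.2.2.1 expects the two reads to differ, since it plans early and late discrepancy rates by arm, but the PFS2 definition takes no account of this.

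PFS2 sits in the alpha-controlled hierarchy and controls access to the OS test. If its events depend on which section the programmer follows, the choice could be made in an open-label trial after data have accrued. There is also a data-collection risk. If sites started the 8-weekly review only after the BICR event, as Section 11.1.2.2 says, a second progression before that date might not be recorded, and no later derivation rule could recover it.

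**Working it through.** **1. The plan's own figures.** With 2:1 allocation, HR 0.635, two-sided 5% and 90% power, the required events are (1.960 + 1.282)² / [(2/3)(1/3)(ln 0.635)²] = 10.51 / 0.0458, which rounds up to 230, as stated. For PFS2 with O'Brien-Fleming-type spending at information 180/255 = 0.706, the first boundary is one-sided 0.0076 (HR 0.681) and the final one 0.0227 (HR 0.767). The plan states 0.007 (0.68) and 0.023 (0.77). The design figures are sound; the problem is which dates feed them.

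**2. Which event the definition selects.** Let I1 and I2 be the investigator's first and second progressions and B the BICR progression. The intended PFS2 event is I2, or death if earlier.

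| Order | Event selected by the literal text | Result |
|---|---|---|
| I1 ≤ B < I2 | I2 | as intended |
| B < I1 | I1 can qualify as the progression after B | too early |
| B on or after I2 | a later progression, or death | true second progression skipped |
| B never occurs, or I1 falls after central review ends | no anchor in the definition; death still counts | not covered |

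PFS2 time starts at randomisation, so the date of B does not enter the time. It only determines which investigator record counts, and the result changes only in the last three rows.

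**3. Whether the third row can arise.** RECIST scans are 6-weekly to week 24 and 12-weekly afterwards (Section 3.1); second-progression review is 8-weekly (Section 6.2.5). For an unconfirmed site progression after week 24, the repeat scan is due at the next 12-weekly visit, which can fall after the first 8-weekly review. The schedule therefore permits I2 before B. In the first 24 weeks the 6-weekly scan will usually come first.

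**4. Reach of the end of central review.**
- Patients without a BICR event at the primary cut-off: 310 − 230 = 80 (80/310 = 25.8%). They cannot acquire a BICR-dated first progression once central review has stopped.
- Final PFS2 events in such patients: at least 255 − 230 = 25 (25/255 = 9.8%). Any number of these could be deaths, which count under either anchor, so the guaranteed number of affected events is zero.
- Balance by arm: with exponential PFS, medians of 4 and 4/0.635 = 6.3 months, 22 months' uniform accrual and a 27-month cut-off, the event-free fraction is (e^(−5λ) − e^(−27λ)) / (22λ). With λ = ln 2/6.3 = 0.110 this is about 22% on olaparib; with λ = ln 2/4 = 0.173 it is about 11% on chemotherapy. These inputs imply about 254 events rather than 230, so the percentages are only indicative, but the group is unlikely to be balanced.

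**5. Reach of reader disagreement.** The second and third rows concern patients who have a BICR event, so they lie outside the 80. The protocol gives no disagreement rate and no count of investigator progressions, so no number follows.

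**The case against.** The best defence is that the intention is clear and largely workable. Section 6.2.6 supplies an investigator-determined first progression after the cut-off. Section 6.2.5 already runs the 8-weekly review from the site's progression. In the commonest order of events both anchors give the same PFS2 date. Time to second subsequent therapy or death supports PFS2 without relying on either progression read, and derivation rules for discordant cases could sit in a statistical analysis plan that is not shown.

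Much of this stands, and it rules out several stronger readings:

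- A reader might infer that PFS2 has no usable definition for about a quarter of patients. The documents do not support that. Section 6.2.6 gives an operational rule, deaths count regardless, and the 80 includes patients who may die without progression, be lost or never progress.
- A reader might infer that every centrally unconfirmed progression makes PFS2 one progression late. The shift occurs only if BICR progression falls on or after the investigator's second. Applying an assumed disagreement rate to the 230 would also use the wrong denominator, because those are BICR events including deaths, not investigator progressions.
- A reader might object that the two progressions have different readers. Investigator assessment of second progression is a deliberate choice (Section 12.2, Table 10), not an error.
- A reader might infer that the two PFS2 analyses use different endpoints. Second progression is investigator-recorded at both, and the end of central review cannot affect the first.

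The defence does not remove the conflict itself. Section 11.1.2.2 states a rule, for both the event and the review clock, that Sections 6.2.5 and 6.2.6 contradict. That is an error in the protocol text, not detail left to a later document.

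**Conclusion.** The point holds as a contradiction in the definition of a key secondary endpoint. Followed literally, Section 11.1.2.2 selects the wrong event when BICR progression precedes the investigator's first or falls on or after the investigator's second. It offers no anchor when BICR never confirms or when first progression comes after central review has ended.

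The end of central review bears only on the later PFS2 analysis and on at most about 80 of 310 patients, taking the planned 230 events as met exactly. Reader disagreement can bear on both analyses. The number of patients affected, and the direction and size of any bias, cannot be given from this document. The primary endpoint, its event count and the alpha allocation are not affected. The point matters because PFS2 is a confirmatory test that OS testing depends on.

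**What to change.** Amend Section 11.1.2.2 in three respects, in line with Sections 6.2.5 and 6.2.6:

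1. Define first progression for PFS2 as investigator-assessed RECIST 1.1 progression, at both PFS2 analyses.
2. Define the PFS2 event as the next investigator-recorded progression after that one, or death.
3. Start the 8-weekly second-progression review from that investigator date.

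This gives every ordering of the two reads the same rule and does not depend on central review continuing. The cost is amendment wording and one derivation change. The investigator data are already collected before and after the primary cut-off, and the planned 180 and 255 PFS2 events and the alpha stay as they are. The change should be made before the first PFS2 analysis.
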